**Sessions:**

1. Coping with uncertainty part 1 – deep breathing, mindfulness, anticipatory guidance on common post-CA challenges, provision of informational CA resources
2. Coping with uncertainty part 2 – dealing with anxiety and contradictory emotions
3. Adjusting to CA – acceptance and change coping skills
4. Navigating relationships – effective communication within the dyad and with social supports
5. Meaning, purpose, and gratitude – identifying sources of meaning, purpose, and gratitude
6. Cope ahead after CA – develop individual and dyadic coping plans beyond RT-CA intervention

**Post Program Assessment (30 - 45 minutes)**

This portion of the study will occur after participants have completed the 6-week program. Participants will have the option to complete these questionnaires on a personal computer at home or over the phone with a member of our study staff team. Participants will also complete a 10-30 minute “exit interview” during this time where they can provide feedback for how to improve the program. After the exit interview, we will email the dyad a resource sheet (the same one provided to dyads that screen out) in the event they would like to pursue further emotional support options.

**All measures will be administered at both timepoints unless otherwise stated:**

- Demographics (baseline only)
- Charlson Comorbidity Index (baseline only)
- Barthel Index (survivor only)
- Modified Rankin Scale (survivor only)
- Mini Mental State Exam (survivor only; baseline only)
- Cerebral Performance Category Scale (survivor only)
- Telephone Interview for Cognitive Status (survivor only)
- Clinical Covariates Pre-test (survivor only)
- Clinical Covariates Post-test (survivor only)
- Hospital Depression and Anxiety Scale (HADS)
- Post-Traumatic Stress Disorder Checklist – 5
- The Cognitive and Affective Mindfulness Scale-Revised (CAMS-R)
- ENRICH Social Support Inventory
- Measure of Current Status Part A (MOCS-A)
- Mental Health Resource Usage
- Credibility and Expectancy Questionnaire (CEQ) (original measure administered at pre-test; measure was also adapted to be administered post-test to examine credibility and expectancy after having completed the program).
- Client Satisfaction Questionnaire (CSQ-3; post-test only)
- WHO Quality of Life-Brief
- Dyadic Relationship Scale
- Dyadic Coping Inventory
- Applied Mindfulness Scale
- Preparedness for Caregiving Scale (cargiver only)
- Meaning in Life Questionnaire
- 4 cardiac items from the Anxiety Sensitivity Index
- Gratitude Questionnaire Six Item Form

To understand the CA clinical characteristics of all admitted CA patients at MGH, we also request a waiver of consent to collect the following from the electronic medical record of all logged patients. These characteristics will also be logged for the open pilot patients:

- Cardiac arrest location
- Time until return of spontaneous circulation (ROSC)
- Initial cardiac arrest rhythm
- Age, sex

Each member of the dyad will receive up to \$60 in compensation (\$20 for baseline assessments and \$40 for post-test assessments). Payment will be made as gift cards.

## 7. Risks and Discomforts

Participants may feel uncomfortable when discussing emotions related to CA. As in any research study, there is a small risk that confidentiality may be breached; all efforts to minimize this risk will be taken. In the unlikely event that participants will become suicidal during the duration of the study, the research assistant will contact the PI and appropriate clinical intervention will be executed.

## 8. Benefits

Participants may not benefit from the study directly. However, knowledge from this research study may benefit others by enhancing our understanding of the role of psychosocial skills-based interventions in treating CA survivor-caregiver dyads. Participants may also improve their ability to cope with CA and become more resilient.

## 9. Statistical Analysis

For open pilot quantitative data, we will assess the feasibility benchmarks (recruitment, assessments, adherence, therapist fidelity) and acceptability benchmarks (satisfaction, credibility) (see **Table 1**) through frequencies and proportions. For qualitative data, we will examine exit interviews using thematic analysis. We will then conduct mixed methods analysis using an explanatory-sequential design, which allow us to integrate quantitative and qualitative data to refine the RT-CA manual and study procedures. We will use the exit interviews to explain the open pilot quantitative findings.

**Table 41** Feasibility and Acceptability Benchmarks.

Outcome	Benchmark
Feasibility (>70% Acceptable; >80% Excellent)	
Recruitment	% Eligible dyads who participate
Assessments	% Dyads with no measures missing
Adherence	% RT-CA dyads that complete 4/6 sessions
Therapist Fidelity	% RT-CA selected sessions (20%) (100% adherence on Fidelity Checklist)
Acceptability (>70% Acceptable; >80% Excellent)	
Treatment Acceptability	% RT-CA dyads score above midpoint on Client Satisfaction Questionnaire-3
Credibility and Expectancy	% RT-CA dyads score above midpoint on Credibility/Expectancy Questionnaire
Adverse Events	(Minimal/None)

For contextualizing the clinical cardiac arrest characteristics of our open pilot sample, we will conduct chi square and Wilcoxon rank sum tests for categorical and continuous variables to examine differences in our open pilot sample compared to all MGH cardiac arrest admissions, and all cardiac arrest admissions in the US as reported by the AHA.

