## 2. Specific Aims and Objectives

**Aim 1: Refine RT-CA.** We will conduct a single-arm open pilot of RT-CA (N=5 dyads) to evaluate initial feasibility and acceptability using exit interviews and pre-post assessments.

Findings from Aim 1 will then inform the next iteration of the RT-CA manual and feasibility trial.

**Aim 2: Conduct medical record review** of all admitted cardiac arrest patients at MGH during the study period (N = 200-400). We will collect basic cardiac arrest clinical data on these patients to determine the representativeness of our sample in Aim 1 to all cardiac arrest admissions at MGH and the United States.

Findings from Aim will inform recruitment gaps, if any, and contextualize the recruitment pool at MGH relative to the United States.

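### The Minimal/None adverse-event benchmark cannot be judged as written: no step asks about events, Minimal has no number, and symptom worsening is not examined

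*Combined protocol and SAP*

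**What the plan says.** Section 2 describes a "single-arm open pilot of RT-CA (N=5 dyads", meant to "evaluate initial feasibility and acceptability using exit interviews and pre-post assessments". Safety is not named among the purposes of those assessments.

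Section 9 assesses its benchmarks "through frequencies and proportions" and refers to "acceptability benchmarks (satisfaction, credibility" without naming adverse events. The benchmark table nevertheless has an Adverse Events row with the target Minimal/None. It gives no count, rate, unit (person or dyad), seriousness or relatedness.

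The measures list in Section 6 states: "All measures will be administered at both timepoints unless otherwise stated". It includes "Hospital Depression and Anxiety Scale (HADS" and "Post-Traumatic Stress Disorder Checklist – 5", neither restricted to survivors, but no adverse-event form or question. The session outlines and the exit interview do not mention harms; the interview is for feedback on improving the program.

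Section 7 gives the first risk as follows: "Participants may feel uncomfortable when discussing emotions related to CA". Its only event-specific pathway concerns suicidality and starts once a participant has become suicidal. Appendix A convenes a three-member DMC/DSMB that meets twice a year and can suspend or terminate the study. It lists neither the data the board receives nor any numeric trigger.

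**The concern.** A benchmark needs a way to observe the quantity and a rule for judging it. For adverse events the plan states neither. The count will consist of whatever participants volunteer or staff happen to notice, and a reader could not tell whether, say, two mild events in ten people count as Minimal.

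Events that were not asked about cannot be recovered at analysis, so the error runs one way, towards None. Section 2 says the pilot's findings inform the next version of the manual and the feasibility trial, so any unearned reassurance would carry forward.

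The plan also leaves relevant data unused. The risk it names is emotional discomfort, and it measures anxiety, depression and PTSD symptoms in both members before and after. Section 4 requires only one member to exceed 7 on a HADS subscale at screening. The other can enter at or below 7 and finish above it, and no planned summary would show this.

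**Working it through.** The documents give no adverse-event rate, limit or precision, so there is no planned figure to reproduce. The check has two parts.

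**1. Where could an event be recorded?**

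| Place in the plan | What it provides | Scheduled adverse-event question? |
|---|---|---|
| Section 6, sessions 1 to 6 | Live sessions, recorded for supervision and fidelity | None stated |
| Section 6, measures list | HADS, PCL-5 and Mental Health Resource Usage (both members); Clinical Covariates Post-test (survivor only) | None listed; content of the last two not given |
| Section 6, exit interview | Feedback on the program | None stated |
| Section 6, chart variables | Arrest location, time to ROSC, initial rhythm, age, sex | No |
| Section 7 | Response if a participant becomes suicidal | Reactive only |
| Appendix A | Board review | No data list |

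**2. How much does asking matter?**

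Inputs: n = 5 dyads × 2 = 10 people (Section 2). The per-person event risk p and the chance c that an event is recorded are assumptions, so a range is shown. Independence between people is assumed.

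P(no event recorded) = (1 − p·c)^10

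| Assumed p | c = 1 (all captured) | c = 0.5 | c = 0.25 |
|---|---|---|---|
| 10% | 0.90^10 = 35% | 0.95^10 = 60% | 0.975^10 = 78% |
| 20% | 0.80^10 = 11% | 0.90^10 = 35% | 0.95^10 = 60% |
| 30% | 0.70^10 = 3% | 0.85^10 = 20% | 0.925^10 = 46% |

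If the two members of a dyad always shared the same outcome, the effective n would be 5. At p = 20% the values become 0.80^5 = 33% (c = 1) and 0.95^5 = 77% (c = 0.25).

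**Precision of a zero count with full capture.** The exact one-sided 95% upper bound is 1 − 0.05^(1/n). For 0/10 it is 1 − 0.05^(1/10) = 25.9%; for 0/5 dyads it is 1 − 0.05^(1/5) = 45.1%. The two-sided 95% version for 0/10 is 1 − 0.025^(1/10) = 30.8%.

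**What a countable limit would do with full capture.** With 10 people, P(at least 1 affected) is 65%, 89% and 97% at p = 10%, 20% and 30%; P(at least 2) is 26%, 62% and 85%. These show how a chosen limit would behave and do not recommend one.

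**The case against.** The plan does have safety provisions. Both members attend weekly live sessions that are recorded and supervised, and discussion of difficult cases is one stated purpose. Section 7 covers suicidality in any participant. Mental Health Resource Usage and the exit interview apply to caregivers as well as survivors. A DMC/DSMB with power to stop the study is named, and Appendix A allows a charter to follow, so event procedures may sit in a document not available here. For a five-dyad pilot aimed at refining a manual, this could be thought enough. These provisions stand as mitigation. None states how events are elicited, and a board can review only what has been collected. With two meetings a year, a dyad could complete the 6-week program between them.

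A reader might infer four stronger things that the documents do not support:

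- That the pilot is bound to look safe. The provisions above may bring events to light; the supportable statement is that None may reflect not asking.
- That nothing could capture a caregiver's event. Sessions, questionnaires and the suicidality pathway all reach caregivers; what is missing is a planned question.
- That HADS goes unused. Section 4 uses it for eligibility; what is missing is any analysis of baseline-to-post change for worsening.
- That adverse events are graded by the >70%/>80% bands. The row carries its own criterion in parentheses and the extracted table may have lost its structure, so the row may be a separate section. The analysis text, which confines acceptability to satisfaction and credibility, fits that reading.

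It is also fair that symptom change from hospitalization to the end of the program, without a control arm, cannot separate harm from natural course. That is a reason to keep it apart from the adverse-event count, not a reason to leave it unreported.

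**Conclusion.** The point holds in limited form. One listed benchmark has no stated means of ascertainment and no countable criterion, and the symptom scores that bear on the named risk have no planned summary of worsening.

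The direction of the bias, towards None, follows from the text. Its size does not, because it depends on event and capture rates that the documents do not give. Across assumed risks of 10% to 30%, the chance of recording no event is 3% to 35% with full capture and 46% to 78% if a quarter of events surface, assuming independent participants. Even a fully ascertained 0/10 is compatible with a true risk of up to about 26%, so the count alone would be weak reassurance. The pilot remains feasible. This is worth correcting before enrollment, because the missing information cannot be reconstructed later.

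**What to change.** 1. **Ask.** Put one scripted adverse-event question to both dyad members at sessions 2 to 6 and at post-test. Log event, seriousness and relatedness in REDCap, and state that the DMC/DSMB receives this log.
2. **Count.** Report the number of participants, out of 10, with any event, any serious event and any intervention-related event. State in advance what count of related events qualifies as Minimal, and make clear that the row is not graded by the percentage bands. Beside a zero count, give the exact upper bound (about 26%, one-sided 95%, for 0/10), with the independence assumption noted.
3. **Use the scores already collected.** In a separate descriptive table, not the adverse-event row, show each participant's baseline-to-post HADS and PCL-5 change and the number whose HADS subscale moves from 7 or below to above 7, for survivors and caregivers separately. Note that without a control arm these changes cannot be attributed to the intervention, and that a move from 7 to 8 is only one point.

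The cost is protocol wording, one REDCap form and about a minute per session; item 3 needs no new data. The downside is that the reported event count will probably be higher and less favorable than one based on spontaneous reports.

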Once at the survivor's bedside the RA will explain the study and, if the survivor is interested in participating, will be asked to confirm that they have an informal caregiver (friend or family) that is primarily involved in their care and would be willing to participate. Once they confirm they have an informal caregiver, the RA will conduct emotional and cognitive screening with the survivor (Hospital Anxiety and Depression Scale for emotional distress and Short Form of Mini Mental State Exam for cognitive function). They will then ask permission to contact the survivor's informal caregiver and conduct the same emotional distress screening with the caregiver (either in person or over phone). Only one member of the survivor-caregiver dyad needs to screen in with emotional distress. If either dyad screens in with emotional distress, the RA will then proceed to obtain informed written consent either through paper form or via REDCap e-consent. Both participants that consent via REDCap will be emailed a copy of their signed consent form. The study team will keep track of all survivors and caregivers approached who refuse to participate and their reasons for refusal, as well as survivors that are not eligible to participate. We will also offer to provide survivors and/or caregivers that refuse to participate or screen out with a resource sheet for options to for emotional support should they feel they need it.

**Inclusion/Exclusion Criteria:** Out-of-hospital or in-hospital CA survivor (must have new diagnosis of "cardiac arrest" in electronic medical record from index hospitalization with documented loss of pulse) with an identified caregiver (identified by the survivor who is their primary source of emotional and functional support), 2) survivor must score  $\geq 4$  on Short Form of the Mini Mental State Exam for sufficient cognitive function for meaningful participation, 3) ability and willingness to participate in a hybrid in-person/live video or phone intervention, 4) English speaking adults (18 year or older), 5) at least one member of the dyad endorses clinically significant emotional distress during screening ( $>7$  on Hospital Anxiety and Depression Scale subscales). **Exclusion criterion:** 1) active psychosis, mania, substance dependence, or suicidal intent or plan.

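### Do the two acceptability benchmarks need a stated rule for combining two members' scores, and a named timepoint for the Credibility and Expectancy Questionnaire?

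*Combined protocol and SAP*

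**What the plan says.** The benchmarks table in section 9 has two acceptability rows graded by percentage: the share of "RT-CA dyads score above midpoint on Client Satisfaction Questionnaire-3" and the share of "RT-CA dyads score above midpoint on Credibility/Expectancy Questionnaire". More than 70% is acceptable and more than 80% is excellent. The method is frequencies and proportions. Exit interviews then follow: "We will use the exit interviews to explain the open pilot quantitative findings".

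The measures list in section 6 fixes satisfaction at one timepoint, "Client Satisfaction Questionnaire (CSQ-3; post-test only". The CEQ has two forms: "original measure administered at pre-test; measure was also adapted to be administered post-test to examine credibility and expectancy". The list labels measures that only one member completes, for example "Preparedness for Caregiving Scale (cargiver only", and puts no such label on these two. Compensation is also per person ("Each member of the dyad will receive up to" a stated sum for the two assessments). Each dyad therefore yields two scores per instrument at each administration.

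The only explicit rule in the document for combining the two members' scores is in section 4 and concerns eligibility: "Only one member of the survivor-caregiver dyad needs to screen in with emotional distress". It is not applied to the benchmarks.

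**The concern.** The benchmark counts dyads, but the questionnaires are answered by individuals. A dyad could count when both members are above midpoint, when either is, or when their average is. The CEQ row could refer to the original form at pre-test or the adapted form at post-test. The plan also does not say how to count a dyad with no post-test satisfaction score. Other rows of the same table give a more operational cut, such as a minimum number of sessions.

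With five dyads, one dyad is worth 20 percentage points, so such a choice can move a row from not met to met. Aim 1 (section 2) is to evaluate feasibility and acceptability, and these are its only percentage-graded acceptability measures. If the rule were chosen after the scores were seen, the exit interviews might be explaining a success or a failure that the choice itself produced.

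**Working it through.** **Inputs.** 5 dyads, so 10 members (section 2, Aim 1). Cut-offs of more than 70% and more than 80% (section 9). The plan gives no expected score distribution, so the member rate p and within-dyad correlation r below are assumptions. The plan has no figure of its own to reproduce.

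**Grades.** 3/5 = 60%, not met. 4/5 = 80%, acceptable only, because it does not exceed 80%. 5/5 = 100%, excellent. Meeting the benchmark therefore means at least 4 of 5 dyads.

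**Dyad patterns.** Let a dyads have both members above midpoint, b have one, and c have none, with a + b + c = 5. There are 21 patterns. The both-members rule counts a; the either-member rule counts a + b. They disagree on met versus not met when a ≤ 3 and a + b ≥ 4:

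- a = 0: b = 4 or 5
- a = 1: b = 3 or 4
- a = 2: b = 2 or 3
- a = 3: b = 1 or 2

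That is 8 patterns; the rules agree in the other 13.

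**By number of members above midpoint.** With 7 of 10 above, all 120 placements fail under both-members and pass under either-member. With 8 of 10, 40 of 45 placements give 3/5 against 5/5, and the remaining 5 give 4/5 under each rule. With 9 or 10 of 10, both rules meet the benchmark.

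The 40 of 45 (88.9%) weights placements equally, which assumes that members of a dyad score independently. At p = 0.80 and r = 0.5 a dyad has both above with probability 0.72, one above with 0.16, and none with 0.12. Given 8 of 10 above:

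- three both, two split: 10 × 0.72³ × 0.16² = 0.0956
- four both, one neither: 5 × 0.72⁴ × 0.12 = 0.1612
- chance that the rules disagree: 0.0956 / (0.0956 + 0.1612) = about 37%

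**Chance of meeting the benchmark.** P(both) = p² + r·p(1−p); P(either) = 2p − P(both); then the binomial probability of at least 4 of 5.

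| p | r | P(both) | P(either) | Met, both | Met, either | Gap (points) |
|---|---|---|---|---|---|---|
| 0.80 | 0 | 0.640 | 0.960 | 40.9% | 98.5% | 57.6 |
| 0.80 | 0.5 | 0.720 | 0.880 | 57.0% | 88.8% | 31.8 |
| 0.90 | 0 | 0.810 | 0.990 | 75.8% | 99.9% | 24.1 |
| 0.90 | 0.5 | 0.855 | 0.945 | 84.4% | 97.3% | 12.9 |

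The gap is the chance that the rules disagree, since any result that passes under both-members also passes under either-member. It narrows as members agree more and as scores rise.

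**Timepoint and missing scores.** If 3 of 5 dyads are above midpoint at one CEQ administration and 4 of 5 at the other, the grades are not met and acceptable. This is the 20-point step again and says nothing about which administration is meant. If one dyad is lost before post-test and 3 are satisfied, the result is 3/5 = 60% over all dyads or 3/4 = 75% over those observed. The row's wording most naturally covers all enrolled dyads, and lost assessments already have their own row in the table.

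**The case for a change.** The strongest case for a change is that the remedy is cheap and the possible effect large. Three or four sentences, fixed before scores are reviewed, would remove any suspicion of a convenient rule. At 7 of 10 members above midpoint, the both-members and either-member rules always give opposite answers, whatever the correlation. A reported dyad frequency does not help by itself, because it depends on the rule.

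What stands is that the two rows are not uniquely defined and that the label can differ. The rest carries less weight:

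- The rows can be scored. In the same table the assessments row counts dyads with nothing missing, which is naturally read as covering both members, and a like reading is available here. The CEQ row uses the instrument's unmodified name, which can reasonably be read as the original form.
- The eligibility rule does not show that members will disagree on satisfaction. It concerns distress at screening, and the document does not link the two.
- There are at most ten scores per instrument at each administration. The plan does not promise a listing by member and dyad, but one is easy to give and lets a reader apply any rule.
- Any particular choice, such as both members, the pre-test form, or missing counted as failure, is a preference. Counting missing as failure would also charge dropout to a second benchmark.

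**Conclusion.** No change to the plan is called for. The omission is real: the both-members and either-member rules disagree in 8 of 21 patterns, and under the assumed rates and correlations tabulated the chance of disagreement runs from 12.9 to 57.6 percentage points. But no stated rule gives a wrong result. The design is a single-arm, descriptive pilot of five dyads with no go/no-go criterion. Exit interviews take place whether or not a benchmark is met, and section 6 ties session adjustments to dyads' feedback after the program, not to the grade. A competent analyst would state the dyad rule and the CEQ administration used, keep all enrolled dyads as the denominator, and show survivor and caregiver counts alongside.

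This conclusion rests on the pilot remaining descriptive. If a decision to proceed were tied to these grades, the definitions would need to be fixed in advance.

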#### **4. Subject Selection**

We will recruit and enroll dyads from MGH ICUs and stepdown floors. The majority of cardiac arrest (CA) survivors are initially cared for in the Heart Center Intensive Care Units and stepdown floors, while a minority are also cared for in the Neuro-ICU, Medical Intensive Care Unit, and Cardiac Surgical Intensive Care Unit, and corresponding stepdown floors.

During phase 1 of this study, the PI presented to staff from these ICUs and stepdown floors that care for CA survivors on the overall study aims, purpose, potential benefits to participants, and best ways to facilitate referrals.

Trained study staff will identify new CA survivors primarily through daily pre-screening of ICU and stepdown survivor rosters. We will also obtain referrals from the medical, nursing, or social work team members that are clinically caring for survivors and caregivers on service, whom the PI presented to during phase 1 of the overall study. A new CA survivor is defined as any survivor with a new diagnosis of "cardiac arrest" and documented loss of pulse in their medical record. Study staff will always confirm with a clinical team member about whether screened survivors might be appropriate study candidates before approaching to discuss our study.

Through pre-screening of ICU and stepdown floor patient rosters on Epic, our research assistant (RA) will identify CA survivors and add them to a "cardiac arrest admissions log" stored on REDCap of all CA survivors admitted to MGH during the study period. The cardiac arrest admissions log will serve to aid the RA in monitoring all currently admitted CA survivors' neurological exams to see if they will become eligible for the study. Specifically, the RA will conduct daily review of all currently admitted CA survivors' neurological exam daily as documented in the electronic medical record. The RA will specifically attend to the survivor's documented alertness, orientation, and speech output. The majority of cardiac arrest

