admissions will not regain sufficient neurological function to participate in our open pilot, however, we will keep their basic clinical cardiac arrest characteristics in the admissions log for the duration of the study so that we can then compare our open pilot sample's characteristics to the characteristics of cardiac arrest admissions at MGH, and compare the cardiac arrest admissions at MGH to cardiac arrest patients in the United States. This information is routinely collected and reported in cardiac arrest research. We will need to be able to identify if our enrolled sample is representative of the greater population, and if not, we will need to report the disparities that exist in our enrolled sample.

Should the neurological exam demonstrate focal neurologic recovery (i.e., awake, alert and oriented), the RA will send a Voalte message to survivor's bedside nurse [or other clinician known to the survivor] to confirm recovery of focal neurological status and to ask the survivor for permission to be contacted by our team to explain the study (either in person or over phone if the survivor is discharged before we are able to approach).

Medical and/or social work partners caring for CA survivors that may benefit from our study have volunteered to provide basic information of our study (the same information listed on our study flyer, which they will give to such survivors) and ask the patients for their permission to refer them to us through the Voalte messaging system.

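### Comparing the 5 enrolled survivors with all admissions describes representativeness but is weak support for informing recruitment gaps; low severity, cheap to improve

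*Combined protocol and SAP*

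**What the plan says.** Section 9 (Statistical Analysis) plans two comparisons of arrest characteristics: "we will conduct chi square and Wilcoxon rank sum tests for categorical and continuous variables to examine differences in our open pilot sample", first against all MGH cardiac arrest admissions and then against US admissions as published. It gives no significance level, no power figure and no rule for reading either result.

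Section 2 gives Aim 2 two uses. One is to show how representative the pilot sample is of all MGH and US admissions. The other is in the sentence "Findings from Aim will inform recruitment gaps, if any". Section 4 supports the first use, saying that if the sample is not representative "we will need to report the disparities that exist in our enrolled sample".

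Section 4 also says, of the majority of cardiac arrest patients, that these "admissions will not regain sufficient neurological function to participate in our open pilot". Recovery alone does not make a patient eligible. Among other criteria, the survivor needs a caregiver and a sufficient short-form MMSE score, and "at least one member of the dyad endorses clinically significant emotional distress during screening".

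Much of the information on recruitment is already gathered. Under Section 4, "the RA will conduct daily review of all currently admitted CA" survivors' documented neurological exams, and "The study team will keep track of all survivors and caregivers approached who refuse to participate and their reasons for refusal"; ineligible survivors are tracked too. Table 1 in Section 9 has a recruitment benchmark with eligible dyads as its denominator. Section 6 lists the variables logged for every admission (arrest location, time to ROSC, initial rhythm, age, sex) and says they are logged for the pilot patients as well.

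**The concern.** A recruitment gap is a difference between those who could have been enrolled and those who were. The Section 9 comparators consist mostly of patients who could not have been enrolled. If a logged characteristic is related to neurological recovery, the enrolled group will differ from all admissions even when recruitment is perfect.

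The opposite error is also open. Five survivors give the tests little chance of finding a real difference, and nothing in Section 9 stops a null result from being reported as representativeness.

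What is at stake is the wording of a descriptive conclusion, and any change to recruitment that is based on it.

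**Working it through.** **Inputs.** Enrolled survivors: 5 (Sections 2 and 3). Admissions log: 200-400 in Section 2 and 100-300 in Section 3, so I use 100 to 400 with 200 as the central case. Significance level: not stated; two-sided 0.05 is assumed. Share of admissions recovering, r: below one half by Section 4, with no figure given. Prevalences: none given, so all those below are assumptions. The plan has no power figure to reproduce.

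**Step 1: what the comparison measures.** Let a characteristic have prevalence p_R in recovered and p_N in other admissions. Then p_all = r·p_R + (1−r)·p_N. If the enrolled are a fair sample of the recovered, the expected difference from all admissions is p_R − p_all = (1−r)(p_R − p_N). Because r is below one half, more than half of any recovered/non-recovered difference carries through with no recruitment gap. If p_R = p_N, the effect is zero.

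Illustration with r = 0.3 and N = 200 (rejection rates by exact enumeration):

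| p_R / p_N | Expected difference | Uncorrected chi-square rejects | Fisher rejects |
|---|---|---|---|
| 60% / 20% | 60 − (0.3×60 + 0.7×20) = 60 − 32 = 28 points | 31.7% | 25.0% |
| 20-point pairs, 40/20 to 70/50 | 0.7×20 = 14 points | 7.7-11.0% | 0.4-8.6% |
| equal, at 20%, 40% or 60% | 0 | 2.5-4.1% | 1.1-1.5% |

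**Step 2: power with 5 enrolled.** Power = Σ Bin(i; 5, p1)·Bin(j; n, p2) over all tables with p ≤ 0.05.

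| Contrast | Comparator n | Uncorrected | Continuity-corrected | Fisher |
|---|---|---|---|---|
| 40% vs 20% | 100 | 24.0% | 11.5% | 14.9% |
| 40% vs 20% | 200 | 26.9% | 10.8% | 15.0% |
| 40% vs 20% | 400 | 30.0% | 9.7% | 14.4% |
| 60% vs 40% | 100 | 14.1% | 6.6% | 8.9% |
| 60% vs 40% | 200 | 12.4% | 7.3% | 8.6% |
| 60% vs 40% | 400 | 11.0% | 7.7% | 7.9% |

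One table shows why the test matters. For 3/5 against 40/200, the uncorrected statistic is 205×(3×160 − 2×40)² / (5×200×43×162) = 4.71, p = 0.030. With continuity correction it is 205×(400 − 102.5)² / 6,966,000 = 2.60, p = 0.107. Fisher gives p = 0.063. So 3 of 5 is significant on one test only, while 4 of 5 is significant on all three. At a true 40%, P(3 or more of 5) = 0.317 and P(4 or more) = 0.087, which brackets the power figures at n = 200.

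A larger log does not help, because the 5 set the limit. Rank-sum power for a 0.5 SD shift, 5 against 200, is about 17-18% by simulation. The exact 95% interval for 3/5 alone is 14.7% to 94.7%.

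**Step 3: overlap.** If all MGH admissions include the enrolled, 5 of 200 (2.5%) sit on both sides of a test that assumes independent samples. In the 60%/20% illustration, removing them moves rejection from 31.7 / 10.5 / 25.0% to 32.7 / 13.6 / 27.9% (uncorrected / corrected / Fisher). The effect is small, but the definition should be clean.

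**Step 4: would a recovered-patient comparator isolate the gap?** Suppose 60 of 200 recover, 7 are eligible and 5 enrol (5/7 = 71%, just above the 70% benchmark). Of the 55 recovered but not enrolled, 2 were eligible and 53 were ineligible or unscreened. If the characteristic is present in 60% of the eligible and 50% of other recovered patients, the comparator shows (2×0.6 + 53×0.5)/55 = 50.4%, a difference of 9.6 points with no gap among the eligible. With 40% in place of 50%, it shows (2×0.6 + 53×0.4)/55 = 40.7%, a difference of 19.3 points. Precision is also poor: 3/5 against 33/55 has an exact 95% interval of about −44 to +36 points (score statistic) or −52 to +52 (unstandardised).

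**The case against.** The strongest reply is that the plan never says these tests identify recruitment gaps on their own. Section 9 presents them as context for the sample, and Section 4 states the neurological filter in the same sentence as the comparison, so the comparator was chosen knowingly. Refusal reasons, ineligibility and the eligible-denominator benchmark already address part of the gap question. All of this stands, and it is why the point is minor. What it leaves open is that neither the tracking nor the benchmark shows whether arrest characteristics differ between those enrolled and those lost, and that Section 9 does not say how its results will be read.

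A reader might infer four stronger claims that the documents do not support:

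- **That the comparison is wrong for Aim 2.** It matches the stated representativeness purpose.
- **That false recruitment signals are likely.** The 31.7% rests on an assumed 40-point prevalence difference. With 20 points it is 8-11%, and with equal prevalences there is no bias.
- **That chi-square is invalid here.** In a 2x2 table the enrolled row's expected counts sum to 5, so each is below 5. Even so, null rejection for the uncorrected test is about 3-6% at prevalences of 5-50%. The choice of test affects power more than error control. Continuity correction applies only to 2x2 tables, which means sex and possibly location. Fisher's test is not the usual reading of the plan's wording.
- **That enrolled versus recovered patients would be the recruitment gap.** Step 4 shows that it would not.

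**Conclusion.** The point holds as a cheap improvement of low severity. The comparison with all admissions suits Aim 2's descriptive purpose but gives weak support for informing recruitment gaps. That follows from the plan's own statement about recovery and needs no assumed figure. The size of the eligibility effect is unknown, since the documents give neither a recovery rate nor prevalences.

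The low information in a null result is firmer. It rests on n = 5 and an assumed two-sided 0.05, and holds across log sizes of 100 to 400: power for a 20-point difference is about 10-30% (40% vs 20%) or 7-14% (60% vs 40%). The overlap is a matter of definition with little numerical effect.

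**What to change.** In Section 9:

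1. Exclude the 5 enrolled survivors from the MGH comparator.
2. Make differences with intervals the main result: exact intervals with the method named for categorical variables, and a Hodges-Lehmann shift with a rank-based interval for age and time to ROSC. Any p-values should be secondary and exact.
3. Add: *Differences from all admissions include the neurological eligibility filter. Lack of a statistically significant difference will not be taken as evidence of representativeness.*
4. If a recovery flag may be kept, also tabulate the logged variables for neurologically recovered patients admitted while the pilot was recruiting. Read that table with the tracked refusal and ineligibility reasons, and do not label it the recruitment gap.

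**Cost.** Items 1 to 3 are wording and need no new data. Item 4 needs a flag that is not among the waiver variables listed in Section 6. Section 5 justifies the waiver by the small amount of information reviewed, so IRB confirmation or an amendment may be needed. Intervals will stay very wide because 5 is the limit. Race and ethnicity are not among the logged variables, so none of these changes would speak to the 38% minority recruitment goal in Section 4.
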